7.2.5 Treatment Technique

An immobilization/patient localization system is mandatory for this study. Single isocenter, multi-target, multiple isocenter and non-isocentric techniques are permitted.

7.2.6 Normal Tissue/Critical Structures

The treatment parameters should be modified to optimize the fit of the prescription volume to the target volume while minimizing dose to critical structures. Normal Tissue tolerances are based on *AAPM TG 101*.

- **3 (three) Fraction** Dose Constraints. The maximum point dose to the optic pathway should be less than 17.4 Gy, and <0.2cc will receive 13.8 Gy. No more than 0.5 cc of the brain stem should exceed 18 Gy, maximum point dose 23.1 Gy.
- **5 (five) Fraction** Dose Constraints. The maximum point dose to the optic pathway should be less than 23 Gy, and <0.2cc will receive 20 Gy. No more than 0.5 cc of the brain stem should exceed 23 Gy, maximum point dose 28 Gy.

7.3 Guideline for Unresected Brain Metastases

If all lesions cannot be treated on the same day, all lesions MUST be treated within ≤ 10 days of treatment of the first lesion.

7.3.1 Medications

If single fraction SRS, patients may be given an intravenous bolus dose of 4 to 16 mg of dexamethasone or 40 to 80 mg of SoluMedrol at the time of SRS, at the discretion of the treating physician. Patients in both arms may alternatively be given a short steroid taper over 1-2 weeks, 2-4 mg of dexamethasone twice daily for 5 days, then 2-4 mg daily for 5 days. Concurrent use of a proton pump inhibitor or H2 receptor antagonists are encouraged while on steroids. See Section 8.1 for ancillary/concomitant therapy.

7.3.2 Equipment

Modality: Gamma knife or X-rays with nominal energy of 4 megavoltage (MV) or greater for accelerator-based treatments, including isocentric conical collimators, mini-multi-leaf (5 mm or less) technology, single isocenter multi-target technique, or linear accelerators mounted on robotic arms.

7.3.3 Target Volume Definitions

The volumes shall be defined by typical standard of care MRI brain scan (recommended MR protocol included in Appendix B: IMAGING). ICRU-91 and AAPM TG-263 nomenclature target volumes are defined as follows and will include laterality and tumor location (ie. GTV(#)_frontal_L and PTV(#)_cerebellum_R):

- Gross Tumor Volume (GTV): This is defined as the contrast enhanced tumor seen on planning MRI. The maximal cross-sectional diameter must be < 3.0 cm.
- Clinical Tumor Volume (CTV): The CTV will equal the GTV with no expansion.
- Planning Target Volume (PTV): This is defined as the CTV for this study. Typically there will be no expansion of CTV to create PTV, but an optional 1-2 mm expansion of CTV is allowed when defining the PTV determined by the treating physician based on immobilization and treatment technique.

7.3.4 Target Dose:

Prescription Specification: The dose should be prescribed to the highest isodose line encompassing the PTV, which can range from 45% to 95% of the maximum dose. Dose Definition: Dose is specified in Gray (Gy).

Prescription Dose: For unresected metastases the fractionation schedule should match the fractionation schedule for the surgical bed as treating all lesions at the same time.

Single Fraction SRS. The total prescribed dose is determined by treatment arm and tumor size (maximal diameter).

SSRS Unresected Metastasis:			
Lesions < 1.0 cm receive 24 Gy			
Lesions ≥ 1.0 to ≤ 2.0 cm receive			
22 Gy			

Three Fraction SRS.

FSRS Unresected Metastasis:
Lesion >2.0 cm receive 27 Gy $/3$
fractions

Five Fraction SRS.

Arm B (FSRS) Unresected Metastasis:				
Lesion >3.5 cm receive 30Gy /5				
fractions				

Dose Conformity: The ratio of the prescription isodose volume to the target volume (PTV) should be between 1.0 and 2.0. It is understood that this ratio may be difficult to achieve with some very small lesions. For lesions less than 5 mm in size, a ratio up to 3.0 is acceptable.

7.3.5 Treatment Technique

An immobilization/patient localization system is mandatory for this study. Single isocenter, multitarget, multiple isocenter and non-isocentric techniques are permitted.

7.3.6 Normal Tissue/Critical Structures

The treatment parameters should be modified to optimize the fit of the prescription volume to the target volume while minimizing dose to critical structures. The dose constraints depend on the fractionation schedule utilized.

- Single (one) Fraction Dose Constraints. The maximum point dose to the optic pathway should be less than 9 Gy. No more than 1cc of the brain stem should exceed 12 Gy.
- 3 (three) Fraction Dose Constraints. The maximum point dose to the optic pathway should be less than 17.4 Gy, and <0.2cc will receive 13.8 Gy. No more than 0.5 cc of the brain stem should exceed 18 Gy, maximum point dose 23.1 Gy.
- 5 (five) Fraction Dose Constraints. The maximum point dose to the optic pathway should be less than 23 Gy, and <0.2cc will receive 20 Gy. No more than 0.5 cc of the brain stem should exceed 23 Gy, maximum point dose 28 Gy.

Please refer to the table in Section 7.2.6 for the standard naming convention for critical structures.

Dietary Interventions (16 weeks): Four to seven days prior to the baseline testing, participants in both the Ketogenic and AICR Diet groups will be provided with meals consistent with their diet group that will provide 100% of caloric needs to assist participants with their dietary transition and to ensure participants in the ketogenic arm get into nutritional ketosis by the time of baseline treatment. Food for both diet groups will be provided by a 'ready to eat' meal delivery company along with supplemental snacks. After baseline testing both groups will be provided individualized counseling and support to follow guidelines for each respective eating pattern to maintain their respective diet for the remainder of the study. The Ketogenic Diet will consist of <50 g carbohydrate (personalized based on level of ketones checked daily by finger stick), ~15-20% protein and ~70-75% fat. Total energy intake will be ad libitum to permit overweight/obese participants to restrict caloric intake to induce weight and fat loss for those who are overweight. Participants will be provided with a handheld glucometer (Precision Xtra, Abbott Nutrition) and ketone test strips in order to check the concentration of BOHB from a finger stick. Normal levels of ketones in a person consuming more than 100 grams of carbohydrate per day is <0.1 mmol/L. The goal of the diet will be to induce a state of nutritional ketosis defined as blood ketones >0.5 mmol/L. We believe that a level of ketones above 1.5 mmol/L will enhance the metabolic therapy and deliver better outcomes based on preliminary studies in women with breast cancer (Fine et al., 2012; Schmidt et al., 2011) and blood BOHB concentrations shown to inhibit histone deacetylases (Shimazu et al., 2013b). The carbohydrate level required to induce nutritional ketosis will vary from person to person and thus objective feedback provided by testing blood ketones is a novel tool we will use to personalize the diet by titrating the carbohydrate and protein intake to the participant's individual ketosis threshold. We will encourage consumption of a wide range of ketogenic-appropriate whole foods including non- starchy vegetables, fruits (berries, olives, tomatoes, lemons/limes), meats (beef, chicken, pork, fish, lamb), nuts and seeds, oils (olive, canola, coconut), cheese, butter, cream, and eggs. Contrary to the misconception that the diet is boring or overly restrictive, it is noteworthy that even the most carbohydrate intolerant person can choose from a wide range of whole foods including berries and a wide assortment of vegetables.

Participants randomized into the AICR arm will follow the "Model plate for a cancer preventative diet" which is outlined as follows: "Aim for meals made up of 2/3 (or more) vegetables, fruits whole grains or beans and 1/3 (or less) animal protein. If you are overweight, consider gradually reducing that number. Controlling portion size at home and in restaurants makes a long-lasting difference in controlling your weight."

Adherence and Retention: Achieving good adherence and retention is one of the most challenging aspects of prospective diet intervention studies. Most studies of low- carbohydrate ketogenic diets have poor compliance because of poor understanding of proper formulation and implementation challenges. Historically we have had excellent compliance and satisfaction to a ketogenic diet in both feeding and free-living studies. Ketogenic diets should not be forced on people so we carefully explain details of the diet (including meal plans, acceptable and non-acceptable foods, etc.) so that individuals are knowledgeable about what to expect and can make an informed choice whether to enroll in a study. We have performed multiple ketogenic feeding experiments including a recently completed study at OSU where we observed excellent adherence as determined by daily capillary BOHB measurement over a 10-week period and another ongoing trial in patients with metastatic breast cancer. The proposed study will be the first time we work specifically with cancer patients who are undergoing radiation therapy. We acknowledge there may be unique challenges in regard

to compliance in this population of patients with metastatic cancer due to their cancer diagnosis and/or drug-induced effects on appetite and preferences for food.

Due to the small sample size proposed (n=24), we will have an enhanced researcher/participant relationship to promote individualized education and counseling to facilitate nutritional ketosis and perceived benefit. We have developed extensive educational materials and resources to help participants successfully make the behavior change to eating a very low-carbohydrate diet and an AICR diet. Well-formulated ketogenic diets are unique when compared to other diets in that there exists an ability to receive direct feedback on participant adherence via finger prick and handheld glucometer that measures the biomarker BOHB. Enrolled participants will be in daily correspondence with research staff throughout the duration of the study to provide a personalized nutrition approach and optimize the amount of time spent in nutritional ketosis and to provide continued support and education for the AICR cohort.

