7.1 Treatment considerations

7.1.1 Prior to Treatment

After informed consent is obtained from the patient and prior to randomization, baseline QOL and functional independence assessments must be completed.

The SRS dose has been selected in order to provide a high rate of local control with minimum risk of radionecrosis. The SRS dose is decreased modestly for larger lesions in order to account for the volume effect on complication rates. While prior SRS to other lesions is allowed, repeat SRS to the same lesion/location is NOT allowed.

Treatment Timing: Patients must initiate radiosurgery treatment ≤ 14 days after registration. Treatment should occur within 14 days of the MRI for treatment planning.

Cytotoxic Chemotherapy is not allowed 3 days before SRS, the same day as the SRS, or 3 days after the completion of the SRS.

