8.1 Clinical assessments

Standard of Care Clinic Visits

Participants will be evaluated in the clinic prior to the start of therapy and study intervention, as well as at monthly intervals for history, physical examination for vitals, height, and weight. Hearth Hope Index (HHI), SF-36, cancer specific FACT-surveys, Brief Pain Inventory, and Brief Fatigue Inventory, and self-report diaries (adverse events, adherence and palatability surveys) will be completed to evaluate QOL and will be administered at baseline, monthly during the intervention and at study terminus. Serum or plasma-based biological markers will also be collected at baseline, and midpoint and study terminus. Standard of care brain imaging will be utilized at baseline, 8 and 16 weeks to evaluate disease status and progression. Body composition and bone mineral density will be assessed at baseline and 16 weeks using dual energy x-ray absorptiometry (DXA).

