9.0 BIOCHEMICAL, COGNITIVE AND PSYCHOSOCIAL TESTING

Activity Monitor:

Physical activity during a course of radiation therapy can be associated with decreased fatigue and may potentially mitigate other side effects. An activity tracker will be worn around the wrist daily for heart rate and step counting.

Peripheral Blood Samples:

Additional lab samples, which are not part of standard care, will be obtained at baseline and paid for as a research cost. Blood will be collected at baseline and every 8 weeks throughout the study duration until terminus.

Continuous Glucose Monitoring (CGM)/ Continuous Ketone Monitoring (CKM):

In order to more accurately quantify the glycemic control and diet adherence of patients using either the AICR or Ketogenic diet we will use three 10-14 day recording periods of CGM/CKM at baseline, midpoint and post-testing. A small Bluetooth compatible unit will be affixed to either the triceps or adipose located near anterior superior iliac spine. CGM/CKM will be analyzed for glucose excursions, mean glucose levels and other markers of glycemic control.

Insulin Resistance and Pre-Diabetes Panels

Due to the high correlation between insulin resistance, diabetes and breast cancer occurrence/prognosis, we will examine the effects of the two diets on several biomarkers including HbA1c, Insulin, Glucose, and Sex hormone binding globulin (SHBG).

Inflammation Panel

Due to the fact that anti-cancer therapies result in increased inflammation, we will examine a panel

of inflammation markers. Each of the following markers is associated with either prognosis or quality of life. The markers to be assessed will be: $TNF-\alpha$ IL-6, IL- 8, CD-14, and CD-16.

Collection and Handling of Specimens

At baseline, and on a monthly basis until study terminus blood will be collected from the participant. Prior to testing all vacutainers will be labeled per study requirements. Blood will be collected into vacutainers, inverted and then stored depending on requirements for each assay.

Cognitive Testing

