13. CRITERIA FOR RESPONSE ASSESSMENT

All patients who took the intervention for any period of time will be considered evaluable. Participants with only baseline measures and who did not receive the intervention will be considered as drop-outs. RECIST v. 1.1 will be utilized to evaluate responses to therapy.

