17.0 STATISTICAL ANALYSES

Analysis Plan

Unless otherwise specified, all analyses will proceed on an intent-to-treat basis, and hypothesis tests will be two-sided and at the 5% significance level.

The primary objective is to assess the feasibility of maintaining a ketogenic versus AICR diet in patients with brain metastasis selected for radiosurgery. The primary measurements are blood levels of glucose and ketones. Measurements will be taken at baseline, 8 weeks, and 16 weeks. These biomarker outcomes will be analyzed using mixed effects linear regression with fixed effects for timepoint, diet group, their interaction, BMI, and sex. We will use subject-level intercept random effects to account for correlation between repeated measurements within subjects. The primary targets of inference are the treatment effects at each (post-baseline) timepoint. To test the two primary measurements at the two post-baseline timepoints, we will use a 4-way Bonferroni-Holm correction to account for multiplicity. Retention at week 8 and 16, as well as side effects, will be summarized and compared between diet groups.

To assess the preliminary efficacy of ketogenic versus AICR diet on tumor response to targeted radiation therapy, we will use a Chi-squared test for the association between treatment group and partial-or-complete response according to RECIST v1.1.

For the exploratory objective assessing the preliminary effects of the ketogenic versus AICR diet on quality of life in BM individuals undergoing radiation therapy, we will use the same linear mixed effects model as for the primary objective, but with the following quality-of-life endpoints as outcomes: Hearth Hope Index, SF-36, FACT-B, Brief Pain Inventory, and Brief Fatigue Inventory. Tests will be performed without multiplicity correction.

The mixed models used for the primary analyses are applicable to unbalanced data due to chance imbalances, missing data, or drop-out. We will assess the possible impact of non-random missingness using sensitivity analyses.

Power Analysis

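### The protocol does not secure a pre-diet glucose or ketone value: read literally, the baseline of both primary endpoints is taken after 4-7 days on the randomised diet

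*Protocol*

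**What the plan says.** All references are to the protocol.

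- **Dietary Interventions (16 weeks), printed after Section 7.3.6.** "Four to seven days prior to the baseline testing, participants in both the Ketogenic and AICR Diet groups will be provided with meals" matching their diet group and covering full caloric needs. One stated purpose is "to ensure participants in the ketogenic arm get into nutritional ketosis by the time of baseline treatment". Individual counselling follows baseline testing. This is the only text that orders the diet against baseline testing, and it puts the diet first.
- **Section 5.0.** Circulating glucose and circulating ketones are the primary endpoints.
- **Section 17.0, Analysis Plan.** "Measurements will be taken at baseline, 8 weeks, and 16 weeks". The mixed model has timepoint, diet group, their interaction, BMI and sex. "The primary targets of inference are the treatment effects at each (post-baseline) timepoint".
- **Section 17.0, Power Analysis.** The 99% power is stated for differences between arms in mean change.
- **Section 7.1.1.** "After informed consent is obtained from the patient and prior to randomization, baseline QOL and functional independence assessments must be completed". Glucose and ketones are not named.
- **Section 8.1.** "Participants will be evaluated in the clinic prior to the start of therapy and study intervention". That sentence covers history, examination, vitals, height and weight. Blood markers come in a separate sentence and are timed only as baseline, midpoint and end.
- **Section 9.0.** For continuous glucose and ketone monitoring (CGM/CKM), "we will use three 10-14 day recording periods of CGM/CKM at baseline, midpoint and post-testing". When the baseline recording starts relative to the diet is not stated.
- **Section 13.** "Participants with only baseline measures and who did not receive the intervention will be considered as drop-outs".
- **Section 14.** Consent, blood tests, CGM/CKM and the ketone finger stick share one week 0 column.

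**The concern.** The lead-in meals differ by arm, so randomisation has already taken place when they start. For ketones, the lead-in is meant to move the endpoint before it is first measured. If the sites follow the dietary section literally, the trial has no off-diet reference for either primary endpoint.

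Two things would be lost. The change in glucose and ketones produced by the diet could not be described from its true starting point. And the quantity on which the trial is powered, the arm difference in mean change, would start from a point already inside the intervention.

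This is a matter of conduct, not of analysis. A statistical analysis plan can choose a contrast or a covariate, but it cannot supply a blood value that was never drawn.

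**Working it through.** **1. Do the sections settle the timing?**

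| Section | Bearing on baseline | Fixes glucose or ketones before the diet? |
|---|---|---|
| Dietary Interventions | Study meals 4-7 days before baseline testing | No; places them after diet start |
| 7.1.1 | Before randomisation | No; quality of life and function only |
| 8.1 | Before therapy and intervention | No; clinic evaluation only, blood timed as baseline |
| 9.0 | Blood and CGM/CKM at baseline | No; start not given |
| 13 | Some participants have baseline measures but no intervention | No; implies an earlier baseline but names no measure or time |
| 14 | Consent and blood tests both at week 0 | No; no order within week 0 |

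The dietary section conflicts with what Sections 8.1, 13 and 14 suggest, and no section secures a pre-diet value.

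**2. Reproducing the stated power.** Inputs from Section 17.0: n = 12 per arm, two-sided alpha 0.0125, SD of change 1.077 mg/dL (glucose) and 0.16 mmol (ketones), differences 2.3 mg/dL and 0.34 mmol.

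Noncentrality = difference / (SD × √(2/n)), with 22 degrees of freedom and critical value 2.720.

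- Glucose: 2.3 / (1.077 × 0.4082) = 5.23, power 99.1%.
- Ketones: 0.34 / (0.16 × 0.4082) = 5.21, power 99.0%.

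Both agree with the stated 99%.

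**3. What an on-diet baseline does to a change contrast.** Illustration for ketones only. Assumptions: 0.1 mmol/L before the diet and 0.5 after the lead-in (the usual-diet and ketosis levels in the dietary section, which are not measurements at 4-7 days); AICR arm flat at 0.1; SD held at 0.16.

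Missed effect = 0.5 − 0.1 = 0.4 mmol, whatever the follow-up level. True effect = follow-up − 0.1. Remaining change = follow-up − 0.5.

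| Follow-up (mmol/L) | True effect | Remaining change | Share missed | Power on change |
|---|---|---|---|---|
| 0.7 | 0.6 | 0.2 | 67% | 64% |
| 0.8 | 0.7 | 0.3 | 57% | 96% |
| 0.9 | 0.8 | 0.4 | 50% | 99.9% |
| 1.0 | 0.9 | 0.5 | 44% | over 99.9% |

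The 0.7 row corresponds to the preliminary mean change of 0.6 mmol (0.1 + 0.6), if that change was measured from an off-diet baseline, which Section 17.0 does not say. The 1.0 row is the level above which Section 8.2 counsels participants to aim.

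The result also depends on how much arises in the lead-in. For a true effect of 0.6 mmol, missing 0.2 leaves 0.4 (99.9%), missing 0.3 leaves 0.3 (96%), missing 0.4 leaves 0.2 (64%) and missing 0.5 leaves 0.1 (14%).

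**4. Level contrast.** The arm difference at follow-up does not involve the baseline value. In the 0.7 row it is 0.7 − 0.1 = 0.6, with nothing lost.

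**5. Glucose.** The protocol gives no glucose response at 4-7 days, so no loss can be calculated.

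**The case against.** The strongest reply is that the primary inference is unharmed. Section 17.0 targets effects at the post-baseline timepoints, and baseline is an outcome row in the model, not a covariate. The objective is the feasibility of maintaining a diet, which levels at weeks 8 and 16 answer directly. The t-test on changes is a planning approximation; the protocol itself says the mixed-model tests should do slightly better. This stands. A reader might infer that the primary comparison is biased or that the trial is underpowered; the documents support neither. The 64% needs follow-up ketones of only 0.7 mmol/L, and at the counselled level power on the change scale stays above 99.9%.

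A reader might also infer that adjusting for an on-diet baseline would damage the primary result. The protocol plans no such adjustment, and the size of the effect depends on an assumed within-subject correlation. In the 0.7 scenario the adjusted difference is 0.6 − 0.4 × correlation: 0.52, 0.40 and 0.28 at correlations of 0.2, 0.5 and 0.8.

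Secondly, the text may lean towards a pre-diet baseline. The drop-out definition in Section 13 makes sense only if baseline can precede the diet. Section 14 puts consent and blood tests in the same week, and arm-specific meals cannot precede consent. It also schedules the food questionnaire and 3-day log only at week 0, which suggests a record of usual eating, though the note to its asterisk is not visible. Baseline testing in the dietary section may be loose wording for the radiosurgery date. Practice may therefore be sound, and an established design error cannot be claimed. But these are inferences. None fixes the sample time, and the one explicit ordering points the other way.

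Thirdly, the choice of contrast and covariates is commonly left to the statistical analysis plan, which is not at hand. This is accepted; only the sample timing and the definition of baseline belong here.

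**Conclusion.** The point holds in limited form and should be fixed. The protocol contradicts itself on when baseline falls and does not secure a pre-diet value of either primary endpoint.

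The consequence is confined to change from baseline, including the scale of the power statement. There the estimate would be too small by whatever arose in the lead-in: 0.4 mmol for ketones under the stated assumptions. Material loss of power arises only if follow-up ketones stay low relative to the lead-in rise.

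Confidence is medium, because actual practice may differ from the literal wording and the early ketone response is assumed.

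**What to change.** - Draw the already planned baseline blood sample and take the finger-stick glucose and ketone reading after consent and before the first study meal. Define this as the baseline to which the changes in the Power Analysis refer.
- Label any later value taken before radiosurgery as an on-diet run-in value.
- Reconcile Sections 7.1.1, 8.1, 9.0, 13 and 14 and the Dietary Interventions text on when baseline falls. For CGM/CKM, state when the baseline recording starts relative to the first study meal.
- Leave covariates and the exact contrast to the statistical analysis plan.

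**Cost.** This is an amendment to timing wording. The sample, meters and strips are already planned, so no new assay is needed unless a run-in sample is also kept. Baseline would sit 4-7 days further from radiosurgery, and the draw must fit the 14-day window from registration to radiosurgery in Section 7.1.1. It may need a separate visit if it cannot be combined with consent or screening. The baseline CGM/CKM record may remain partly on-diet.

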8.2 Adherence

Participant adherence with the study intervention will be encouraged and monitored in several ways. All participants will be provided a handheld glucometer (Precision Xtra, Abbott Nutrition) and reagent strips that measure BOHB from a small amount of blood obtained by finger stick. Although there is variability between people, BOHB levels in individuals consuming more than 100 grams of carbohydrate per day are usually ≤ 0.1 mmol/L. A primary goal of the initial diet intervention is for each participant to enter nutritional ketosis, which starts at 0.5 mM and extends up to approximately 3.5 mmol/L. This is a strong indication that fat is being used as one's primary fuel, and there may be other therapeutic benefits associated with ketones in this range. Transient increases in ketones above 3.5 mmol/L may occur after exercise, but regulatory feedback systems keep ketones from elevating to dangerous levels that are seen in uncontrolled type-1 diabetics who have insufficient insulin (i.e., >10 mmol/L). Participant's information will be kept private and only made available to IRB approved research staff. During the intervals between research- based visits participants will report their ketone levels daily to the research coordinator and lead RD on the team and adjustments to the diet made accordingly.

We will counsel patients to aim for a level > 1.0 mM while following principles of a well-formulated ketogenic diet. If ketone readings are lower than 0.5 mM, we will individually work with the patient to identify appropriate changes to their diet/lifestyle to achieve nutritional ketosis. The monitoring of daily ketones for patients on the ketogenic diet provides a gold-standard biofeedback marker that is objective and quantifiable for adherence. Deviation from the dietary standards of a well-formulated ketogenic diet will cause rapid decreases in ketones and elevations in blood glucose,

which will be identified in the patient:researcher interaction. For the standard diet arm, this will present a greater challenge. We will ask participants to inform us of dietary deviations and these will be identified and logged. The monthly self-report diaries will be used for tracking any minor adverse effects (GI distress, bloating, gut distension, diarrhea etc.). If participants do not experience any side effects, it is possible they will not have a self-report diary to share monthly.

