8.4 Safety Monitoring

Adverse events will be monitored by self-reporting of signs and symptoms. Patients will maintain weekly contact with researchers and any possible ill effects will be noted and discussed with the attending physician or Research Nurse to discuss and manage any possible side effects. Patients will be counseled with regard to potential signs of treatment toxicity and should immediately contact the PI, study coordinator or treating physician in the event such a problem arises.

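### Counselling aims at perceived benefit alongside ketosis, and diet follow-up is triggered differently by arm: a risk of expectation and ascertainment bias in the retention, side-effect and self-report comparisons

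*Protocol*

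**What the plan says.** The Adherence and Retention paragraph explains that the small sample allows a closer relationship between staff and patient, whose stated purpose is "individualized education and counseling to facilitate nutritional ketosis and perceived benefit". The same paragraph sets the contact: "Enrolled participants will be in daily correspondence with research staff throughout the duration of the study". That sentence gives two reasons, a personalised approach that maximises time in ketosis and, for the other arm, "to provide continued support and education for the AICR cohort".

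Section 8.2 describes how adherence is followed. Between visits, "participants will report their ketone levels daily to the research coordinator and lead RD on the team", and the diet is adjusted accordingly. "If ketone readings are lower than 0.5 mM, we will individually work with the patient", with the stated goal of reaching nutritional ketosis. For the comparison arm the section concedes that monitoring is harder and says: "We will ask participants to inform us of dietary deviations and these will be identified and logged". Minor adverse effects are tracked in monthly self-report diaries, and the section accepts that a participant without side effects may have no diary to hand in.

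Section 8.4 bases adverse-event monitoring on self-report and adds: "Patients will maintain weekly contact with researchers and any possible ill effects will be noted". Section 11 adds that toxicity is graded with CTCAE at study visits and telephone calls, with attribution by the treating physician.

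Section 17.0 compares retention at weeks 8 and 16, and side effects, between the diet groups. It tests the Hearth Hope Index, SF-36, FACT-B, Brief Pain Inventory and Brief Fatigue Inventory between arms as exploratory outcomes without multiplicity correction. The primary measurements are blood glucose and ketones.

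**The concern.** Two features of conduct differ by arm and act on outcomes that the arms are then compared on.

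The first is expectation. Perceived benefit is named as an aim in the same clause as ketosis, and no matching aim is stated for the AICR arm. Patients know their diet, so nothing masks the message. Willingness to stay, readiness to report a complaint, and ratings of hope, pain and fatigue can all shift with what a patient has been led to expect.

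The second is ascertainment. A ketone reading can open an extra conversation with a ketogenic patient. The AICR arm has no equivalent trigger. If side effects come up in such conversations, the chance of capturing them depends partly on arm.

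Retention and side effects are listed endpoints of the primary objective in section 5.0, and in a feasibility pilot they are among the results most likely to be carried forward. Analysis cannot later remove unequal elicitation or a promoted expectation. This is a matter of protocol conduct rather than a detail for a statistical analysis plan.

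**Working it through.** No arithmetic sizes this point, so the check sets the texts side by side.

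1. **The plan's own figure.** The only power statement (section 17.0) is 99% with 12 completers per arm at two-sided alpha 0.05/4 = 0.0125. The noncentrality is difference / (SD × √(2/12)). For glucose this is 2.3 / (1.077 × 0.408) = 5.23, and for ketones 0.34 / (0.16 × 0.408) = 5.21. With 22 degrees of freedom the noncentral t gives 99.05% and 98.99%, so the figure reproduces. It concerns the two blood measurements only and does not bear on retention, side effects or the scales.

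2. **Is perceived benefit tied to one arm?** The clause pairs it with nutritional ketosis. Section 7 (Dietary Interventions) makes ketosis the goal of the ketogenic diet; the AICR diet is a plate model with no ketone target. The AICR cohort is offered support and education, with no mention of perceived benefit. As worded, the aim therefore falls on the ketogenic arm.

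3. **Is staff follow-up triggered alike?**

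| | Ketogenic arm | AICR arm |
|---|---|---|
| Signal of non-adherence | Daily ketone reading | Participant tells staff of a deviation |
| Stated staff response | Diet adjusted; individual work below 0.5 mM | Deviation identified and logged |
| General support | Daily correspondence, individualised counselling | Daily correspondence, individualised counselling |

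   Section 8.2 gives meters to all participants and does not literally confine ketone reporting to one arm. However, the response to a low reading exists to achieve ketosis, so it has a purpose only in the ketogenic arm. The first two rows differ; the third does not.

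4. **How are side effects captured?** By self-report (section 8.4), diaries (sections 8.1 and 8.2), and CTCAE grading at visits and calls (section 11). None of these names an arm. None states a fixed question asked of everyone on a fixed schedule. Because section 8.2 allows no diary when there are no side effects, a missing diary cannot be told apart from a symptom-free month.

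5. **Which comparisons are exposed?** Retention is exposed to expectation, side effects to expectation and elicitation, and the five self-report scales to expectation. Glucose and ketones are measured in blood and are not open to reporting bias.

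6. **Direction.** Promoted expectation could make ketogenic patients report fewer complaints. Extra conversations could make them report more. The text does not say which would prevail, and the documents contain no figure from which either could be estimated.

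**The case against.** The strongest reply is that the two arms get equal contact. A reader might set daily correspondence against weekly safety contact and infer that the ketogenic arm is seen far more often than the AICR arm. The documents do not support that. The daily-correspondence sentence expressly covers the AICR cohort, section 7 gives both groups individualised counselling, and sections 8.4 and 11 apply to all patients. Nor do the two frequencies strictly conflict: one concerns nutrition support and the other safety, and daily contact satisfies a weekly minimum. The ratio of the two schedules is not a between-arm difference. This part of the objection stands in full.

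A reader might also take the AICR arm to be followed only when patients call in. That goes too far as well. Staff ask for the reports, daily correspondence gives an occasion for them, and reliance on the participant concerns deviations only.

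It can further be said that ketone-guided coaching is part of the intervention, so matching the duration and channel of contact would be a design preference rather than a correction. That also stands, and no such matching is asked for here. Finally, the clause states an aim of counselling rather than an instruction on collecting outcomes, retention and side effects carry no success threshold, and quality of life is exploratory. These points limit the consequences. They do not answer the wording on perceived benefit, the different triggers for follow-up, or the lack of a common elicitation of side effects. Neither diet requires any of these.

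**Conclusion.** The point holds as a risk of expectation and ascertainment bias, of unknown size and direction, in the between-arm comparisons of retention, side effects and the exploratory self-report scales. It rests on three readings of the text: that perceived benefit, being paired with ketosis, is aimed at the ketogenic arm; that patients know their diet; and that side-effect capture relies substantially on self-report without a fixed common question. It does not extend to reporting bias in the glucose and ketone measurements. It does not show that bias will occur, or that the arms are contacted at different frequencies. The daily and weekly statements need aligning for clarity, as an ambiguity of purpose rather than a contradiction.

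**What to change.** 1. In the Adherence and Retention paragraph, delete the closing words *and perceived benefit*, and require neutral wording about expected benefit in both arms.
2. In sections 8.2 and 8.4, use the weekly safety contact already planned to ask the same scripted side-effect and diet-deviation questions in both arms, and record 'none' explicitly, so that an absent diary is no longer read as an absence of events.
3. State which contact serves which purpose: daily correspondence for nutrition support in both arms, weekly contact for safety.
4. Leave arm-specific dietary coaching, including ketone-guided follow-up, unchanged.

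The cost is a few sentences of protocol text, a short script, and slightly more recording by staff at contacts that are already planned.
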